4.1.1 Inclusion Criteria

To be included in the insomnia group, participants will need to score ≥ 11 on the ISI (Morin et al 2011), meet RDC (Edinger et al 2004) for insomnia, and have insomnia for 6 months or longer. To be included in the depression and insomnia group, participants will need to meet insomnia criteria and additionally meet criteria for a Major Depressive Episode as assessed by the SCID. To be included in the healthy control group, participants will need to score ≤ 7 on the ISI and not meet RDC for insomnia.

4.1.2 Exclusion Criteria

Exclusionary criteria for all participants will include: age younger than 18 or older than 40; inability to speak, read, and write in English; body mass index > 40 ; history of significant head trauma or loss of consciousness > 30 minutes; a score less than 27 on the Mini-Mental Status Exam (MMSE) (Folstein et al 1975); regular psychotropic medication use within two weeks of beginning the protocol with the exception of those in the depression and insomnia group (these individuals will be allowed to remain on psychotropic medications with the exception of sleep medications or other psychotropic medications with large concern for impacting hdEEG recordings; if participants are on medications of concerns, they will be excluded from the study) (Bastien et al 2003, Borbely et al 1985, Brunner et al 1991, Feige et al 1999, Monti et al 2000); current regular tobacco use; > 3 caffeinated beverages per day; significant neurologic or medical illness, including dementia; women who are pregnant, < 6 months post-partum, or planning to become pregnant during the study; and left-handedness (due to effects on sleep topography). Participants will be excluded if they indicate imminent risk for self-harm or suicide (APA 1994), alcohol or drug dependence/abuse within the last 6 months, or any other primary sleep disorder including apnea, restless legs, circadian rhythm disorder, parasomnia, or primary CNS hypersomnia. To ensure exclusion of participants with a circadian rhythm disorder, all participants must demonstrate a typical sleep phase between 9pm and 9am (confirmed via self-report and actigraphy). To ensure exclusion of participants with sleep apnea, participants must exhibit an apnea-hyponea index (AHI) less than 10 (as assessed via ApneaLink). Participants in the insomnia and control groups will also be excluded if they met criteria for any active DSM-IV Axis I disorder other than insomnia. Participants in the depression and insomnia group will be excluded if they indicate a lifetime history of bipolar disorder or schizophrenia.

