In summary, the use of hdEEG to study sleep in insomnia with and without depression affords a unique opportunity to image the brain with exquisite temporal resolution throughout the sleep period. Not only can we study the spatial and temporal dynamics of sleep throughout the night, but we can also examine the processes of falling asleep and arousing from sleep; these critical events are likely to be particularly important for understanding insomnia, since they reflect the primary complaints of insomnia patients—difficulty falling asleep and difficulty maintaining sleep. No other currently available imaging technique is capable of providing functional imaging data throughout the sleep process or in individuals who can sleep without restriction of their normal nocturnal movement. Furthermore, in contrast to other imaging procedures, hdEEG is relatively inexpensive, portable, and can be performed repeatedly making it ideal for longitudinal studies. Our preliminary data in a small number of subjects already shows significant differences in topographic patterns of sleep EEG activity in comparison not only to healthy sleepers but also depressed subjects, suggesting that the technique will be able to detect abnormalities in brain activity patterns that are specific for insomnia. Even more importantly, we can localize one of these insomnia-specific abnormalities, increases in alpha activity during deep stages of sleep, to sensory areas of the cortex, strongly suggesting that these specific areas remain relatively activated during sleep. The proposed study will provide novel data regarding mechanisms of insomnia and will be used to design future studies that will assess the effects of insomnia treatments on patterns of abnormal brain activity. The identification of specific abnormalities during sleep as well as in the processes of falling asleep or arousing from sleep will potentially allow us to distinguish the effects of pharmacologic treatments that promote sleep through different mechanisms, such as by increasing GABA transmission, blocking histamine receptors or blocking orexin receptors.

3. Specific Aims

3.1. Primary Objectives:

1. Examine differences in the cortical sources of sleep waveforms in insomnia patients with and without depression compared to healthy sleeping controls.

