2. Define cortical source abnormalities in the processes of falling asleep and arousing from sleep in insomnia patients with and without depression compared to healthy sleeping controls.

3.2 Secondary Objectives:

1. Correlate abnormalities in sleep EEG patterns with specific insomnia symptoms, including sleep onset difficulties, sleep maintenance problems, nonrestorative sleep and daytime dysfunction.

Insomnia and Sleep Patterns Study

2. Define abnormalities in overnight changes in waking EEG activity in insomnia patients with and without depression compared to healthy sleeping controls.
3. Explore whether abnormalities in sleep and waking EEG activity in insomnia patients, with and without depression, normalize following treatment with a sleep medication.

3.3 Clinical Hypotheses:

1. Insomnia patients will show increased regional EEG alpha activity in sensory cortical areas particularly during sleep.
2. Insomnia patients will show abnormalities in the process of sleep initiation, including regional sources of high frequency EEG activity that will interfere with the normal progression of the sleep process.
3. Insomnia patients will show abnormalities in the regional patterns of cortical arousal responses to external stimuli during sleep, particularly in the sensory cortical areas exhibiting increased alpha activity.
4. Abnormalities in sleep EEG patterns may be correlated with specific insomnia symptoms, particularly difficulty with sleep initiation or maintenance.
5. Waking EEG in insomnia patients will not show overnight recovery compared to controls, which will be correlated with specific EEG abnormalities during sleep, such as elevations in higher frequency activity.
6. Explore whether insomnia patients with and without depression differ in abnormalities in sleep EEG patterns.

4. Research Design and Methods

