4.1 Study Population

Studies will be carried out in 20 individuals with insomnia, 20 individuals with depression and insomnia, and 20 age- and sex-matched healthy controls (women and men aged 18-45 years who are English speaking). We will ensure that our sample includes individuals with both sleep onset and maintenance issues, and that at least 1/3 of the sample is male. Strict inclusion/exclusion criteria will be applied to the sample to reduce the variability of the data and avoid confounding factors.

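### Only the depression and insomnia group may stay on psychotropic drugs, so contrasts with that group may mix depression with medication, and no planned analysis separates them

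*Combined protocol and SAP*

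**What the plan says.** Section 4.1 sets three groups: "20 individuals with insomnia, 20 individuals with depression and insomnia, and 20 age- and sex-matched healthy controls". It gives the purpose of the eligibility rules: "Strict inclusion/exclusion criteria will be applied to the sample to reduce the variability of the data and avoid confounding factors".

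The exclusions in Section 4.1.2 that apply to all participants include "regular psychotropic medication use within two weeks of beginning the protocol with the exception of those in the depression and insomnia group". For that one group the rule is that "these individuals will be allowed to remain on psychotropic medications". This permission is then limited in the same sentence, which goes on to carve out two kinds of drug: "with the exception of sleep medications or other psychotropic medications with large concern for impacting hdEEG recordings". A participant on a drug of concern is excluded. No list or criterion says which drugs count as large concern.

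The group enters both primary objectives in Section 3.1: "Examine differences in the cortical sources of sleep waveforms in insomnia patients with and without depression compared to healthy sleeping controls", and "Define cortical source abnormalities in the processes of falling asleep and arousing from sleep in insomnia patients with and without depression", again against healthy controls. It also enters Secondary Objective 2 (overnight change in waking EEG). Hypothesis 6 in Section 3.3 is the direct contrast: "Explore whether insomnia patients with and without depression differ in abnormalities in sleep EEG patterns".

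Section 4.4.2 plans SnPM comparisons of source maps, ANOVA with post-hoc corrections, correlations and exploratory Cox regression. It names no medication covariate, stratum, subgroup or sensitivity set.

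**The concern.** In two of the groups, psychotropic use is removed by eligibility. In the third it is allowed, and it can occur only there. If some of those participants are medicated and the drugs shift the sleep EEG, the drug effect and the depression effect enter the contrast together.

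This can mislead in both directions. A drug effect can look like an effect of depression. A drug effect of opposite sign can also hide a real difference, so that insomnia with and without depression look alike. At stake are the answer to Hypothesis 6 and the reading of the depressed-group maps as markers of insomnia with depression, which is part of the goal stated in Section 1.

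**Working it through.** **1. Does anything in the plan separate the two?**
- Matching in Section 4.1 is on age and sex only.
- SnPM, as described in Section 4.4.2, deals with multiplicity and distributional assumptions. It does not deal with imbalance between groups.
- Visits 5 and 6 (Section 4.2.2) repeat recordings after a sleep medication is started. They say nothing about psychotropics taken at baseline.
- The assessment table in Section 4.2.2 lists medical history at Visit 1 and no medication log at any hdEEG night.
- By their titles, the five references cited for the medication rule all concern benzodiazepines, zolpidem or other hypnotics. The documents therefore show no evidence that the permitted drugs are neutral for hdEEG.

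**2. The plan's own figures.** Section 4.4.1 gives d = 1.15 from the insomnia and control pilot, two-sided alpha 0.05, and power of about 94% with 20 per group and 68% with 10 per group. For a two-sample t test the noncentrality is d × √(n1·n2/(n1+n2)):
- 20 v 20: 1.15 × √10 = 3.64, power 94.3%.
- 10 v 10: 1.15 × √5 = 2.57, power 68.2%.

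Both reproduce. Neither concerns a contrast with the depression group, for which no effect size is given.

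**3. Illustration of size.** Let f be the share of the 20 who are medicated and g the drug effect in SD units. Both are assumed. With no true depression effect, the expected bias is f × g. For f = 0.50 and g = 0.5 this is 0.25 SD. Simulated t tests, 20 v 20, nominal 5%, 200,000 runs per setting, gave these rejection rates:

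| Drug effect g | f = 25% | f = 50% | f = 75% |
|---|---|---|---|
| 0.2 SD | 5.3% | 6.1% | 7.5% |
| 0.3 SD | 5.5% | 7.3% | 10.5% |
| 0.5 SD | 6.4% | 11.5% | 20.5% |

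In the masking direction, take a true depression effect of 0.8 SD, half the group medicated and a drug effect of −0.5 SD. The net difference is 0.8 − 0.25 = 0.55 SD, and power falls from 69% to 39%.

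**4. What restriction costs.** Power of the unmedicated depressed participants against 20 others, by the formula in step 2:

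| Unmedicated left | d = 1.15 | d = 0.8 | d = 0.5 |
|---|---|---|---|
| 20 (all) | 94% | 69% | 34% |
| 15 | 90% | 62% | 30% |
| 10 | 82% | 51% | 24% |
| 5 | 60% | 34% | 16% |

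**The case against.** The strongest reply is that the investigators dealt with this through eligibility. Sleep drugs and drugs of large concern are barred. Section 4.2.2 shows the same care at Visit 4, where a depressed participant about to start an interfering drug is not invited. Section 4.4.2 also calls the protocol largely exploratory, involves a biostatistics group and leaves room for further analyses. That stands as far as it goes: the worst drugs are out, and a subset analysis is not ruled out. It does not remove the problem, because large concern is undefined, drugs below that threshold remain in one group only, and no check is specified.

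Four stronger readings are tempting, and the documents do not support them.

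- A reader might infer that every contrast with the depressed group is confounded. Staying on medication is permitted, not required, and no share is given. If nobody were medicated, there would be no confounding.
- A reader might infer that the primary objectives as a whole are compromised. Insomnia alone versus control is untouched. It is the contrast the pilot work leads to (Section 2.2) and the only comparison between study groups with a power figure.
- A reader might assume a drug effect of about 1 SD and obtain very high false-positive rates. That is close to the whole pilot insomnia effect of 1.15, and a drug known to act so strongly ought to fall under the large-concern exclusion.
- A reader might want to credit depression only when the finding is significant in unmedicated participants. Step 4 shows why not: at d = 0.8, power drops from 69% to 51% with 10 left and 34% with 5, so lost power would be read as a drug effect.

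**Conclusion.** The point holds in a limited form. As written, the plan could credit a drug effect to depression, or miss a depression effect, in Hypothesis 6 and in the depressed-group parts of Primary Objectives 1 and 2.

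The size cannot be fixed from the documents. For shares of 25–75% and drug effects of 0.2–0.5 SD, the false-positive rate is about 5–20% instead of 5%; at the low end the harm is negligible. The range rests on assumed values, on every permitted drug acting equally and in one direction, and on a t test of a single summary measure. The plan tests whole source maps by SnPM, so the figures show the order of magnitude and do not predict the error rate of the planned test.

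This is a cheap improvement to the analysis plan. It is not a reason to doubt the design as a whole.

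**What to change.** Keep the eligibility rule and add the following to Sections 4.2.2 and 4.4.2:

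1. Record psychotropic drug and class at each hdEEG night, and add this to the assessment table.
2. Prespecify, before group maps are examined, a sensitivity analysis that repeats each contrast involving the depression and insomnia group with that group restricted to unmedicated participants.
3. Report medicated and unmedicated estimates side by side, with intervals and with the HRSD scores collected at Visit 1.
4. Judge consistency on the size and direction of the estimates, not on significance in the subset. State that a difference seen mainly in medicated participants cannot be assigned to depression alone.

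A medication covariate in the three-group model is not a substitute. Medication varies only within the depressed group, so its coefficient would rest wholly on the medicated versus unmedicated difference there.

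The cost is a short medication record at each night and some extra analysis. There are two downsides. The subset may be small: at d = 1.15, power is 90%, 82% or 60% with 15, 10 or 5 unmedicated participants, against 94% with all 20. Medication status may also track depression severity, so the restricted result is a check and does not cleanly separate drug from illness.

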4.1.3 Subject Identification and Recruitment

Subjects will be recruited via advertisements (i.e., newspaper, internet, newsletters, local postings), referrals from health care providers, referrals from patient advocacy/support groups, and word of mouth. A phone screening will be used to pre-select the subjects eligible to participate before their first visit to our laboratory (see section 4.2.1).

Subjects with insomnia and/or depression will primarily be recruited via advertisements and referrals from local physicians and mental health care providers, including through the UW Sleep Disorders Center and the UW Department of Psychiatry. Clinicians, including investigators involved with this study, may inform their referrals and patients about the study, either verbally or with printed materials approved by the IRB. Patients who may be eligible will also be reviewed through the medical chart. Following the review of their medical record, providers will receive a prompt that the patient is potentially eligible for the study along with a quick checklist of I/E criteria to complete. The prompt will be delivered via HealthLink message, and the checklist will be placed in the provider's clinic mailbox. Providers introducing referrals or patients to the study can provide their patients with the study's contact information to contact us directly themselves or will obtain the patient's permission via permission to contact form prior to providing researchers with contact information. Patients may have the option to meet with study staff face-to-face before leaving the clinic from an appointment with his/her provider (contingent upon study staff availability and patient's preference) versus being contacted by phone for the screening interview. If a potential subject is a patient of one of the investigator's clinic patients, another investigator who does not have a clinical relationship with the subject

Insomnia and Sleep Patterns Study

will conduct the screening interview. The clinical care of the potential subject will in no way be affected by their decision to participate or not. We will also recruit from UW Health clinics and University Health Services. In these settings, flyers will be posted with information about how to contact the study coordinator if interested. Interested individuals will complete the screening interview over the phone to determine initial eligibility and then will be scheduled for a face-to-face screening appointment.

For healthy control subjects, advertising, particularly via posted flyers, electronic newsletters, and other newspaper or internet announcements, will be the primary recruitment method. Subjects who contact the investigators will complete the same screening interview as psychiatric subjects (see section 4.2.1).

4.2 Study Protocol

4.2.1 Screening for Eligibility

Eligibility will be determined through a three-part screening process including a screening interview, baseline screening, and at-home overnight sleep study with actigraphy and sleep logs.

Screening Interview

Interested individuals will first undergo a screening interview to determine initial eligibility for the study. After providing a description of the study procedures, subjects will be asked a series of questions by a study staff member about their physical and mental health, sleep, and other inclusion/exclusion criteria. Screening interview data from subjects who are not eligible or do not ultimately sign a consent/HIPAA form will be destroyed. Some participants will complete this screening in person at a regular clinic visit if their provider refers them to the study and the study team is available. For these participants, verbal consent will be obtained prior to the screening like with screenings completed over the phone. Written informed consent will be obtained for all participants during the baseline screening visit.

Baseline Screening (Visit 1)

This visit will begin with the informed consent process. As part of this consent procedure, participants may give permission for the UW study team to contact them again for participation in future studies. If permission is given, the UW study team will store their names and contact information (i.e., telephone number and/or email address). This information will not be distributed to any other non-UW study entities (e.g., Merck). Participants then will be evaluated for insomnia with RDC criteria and complete the ISI. They will also complete the Edinburgh Handedness Questionnaire (EHQ)(Oldfield 1971), answer some demographic questions, and undergo the Structured Clinical Interview for DSM-IV Axis I Disorders (SCID)(Spitzer et al 1992), MMSE, Hamilton Rating Scale for Depression (HRSD) (Hamilton 1996), and an unstructured clinical interview for sleep disorders, medical disorders and habits. Participants may be audio and video recorded during these assessments except when illicit substance use is assessed to ensure that interviews are valid and reliable. Recordings will only be viewed by study team members and will be kept until completion of the study and then will be destroyed. Height and weight will be collected for all participants. Women will complete a urine pregnancy test and phase of menstrual cycle and birth control medication will be monitored (via self-report) throughout participation in the study. After initial screening, participants will complete

Insomnia and Sleep Patterns Study

[figure not shown]
questionnaire measures of pre-sleep somatic and cognitive arousal (i.e., the Pre-Sleep Arousal Scale, PSAS(Nicassio et al 1985)), thought content when having difficulty sleeping at night (i.e., the Glasgow Content of Thoughts Inventory, GCTI(Harvey & Espie 2004)), negative sleep-related cognitions (i.e., the Dysfunctional Beliefs and Attitudes about Sleep Scale, DBAS (Morin et al 2007)), and general somatic and cognitive arousal (i.e., the Depression Anxiety Stress Scales, DASS (S.H. & P.F. 1995) and Penn State Worry Questionnaire, PSWQ (Meyer et al 1990)). If time permits, we may also administer the University of Pennsylvania Computerized Neuropsychological Panel (Penn CNP) to cover other cognitive domains such as verbal memory, emotion recognition, and abstract reasoning/decision making. Please find a more detailed description of the Penn CNP in the supplemental materials section of the IRB Initial Application. Although all tasks may be administered (all listed in supplemental attachment), the tasks that we most commonly use are highlighted on the first page. This first visit will last approximately 3 to 4 hours.

All study questionnaires will be reviewed by one of the study clinicians (i.e., Drs. [name], [name], or [name]) before the participant departs. If participants report depression and/or suicidality on their study questionnaires or interviews, they will be provided with a list of community resources (see Supplemental Materials) and encouraged to seek outside treatment. If they endorse suicidality that is at a level of imminent risk, they will be directed to the emergency department for hospitalization. Study staff will ensure that the participant reached the hospital via follow-up with the participant and hospital staff. Participants who are referred for depression treatment may still be eligible to participate in our study provided that they continue to meet inclusion/exclusion criteria. However, participants at imminent risk of harm to themselves will not be eligible (as noted in the exclusion criteria).

At-Home Overnight Sleep Study and Actigraphy with Sleep Logs (prior to Visit 2)

Participants will complete an at-home screening test for sleep apnea, using a three channel recording of airflow, respiratory effort and oximetry with the Apnea Link™ (ResMed Corp, Poway, CA). Persons who demonstrate an AHI > 10 will be excluded. Participants who have completed a full clinical sleep study within the past year will not need to complete the Apnea Link procedure and the necessary screening information will be collected from their medical record. Sleep-wake patterns will be evaluated over a two-week period using wrist-worn actigraphy (a wrist-watch-like device that measures activity level; Actiwatch, Respiration Inc, Murrysville, PA) supplemented by sleep-wake logs to confirm self-reported sleep-wake patterns. Activity profiles will be analyzed using Actiware. Of all published quantitative criteria to discriminate those with insomnia from good sleepers, sleep-wake log cut-off values have been the most reliable, even in comparison to PSG (Edinger et al 2013, Lineberger et al 2006). Thus, quantitative criteria derived from sleep-wake logs will be used to classify whether insomnia participants have sleep initiation (i.e., an average of 20 minutes or greater of SOL) or sleep maintenance insomnia (i.e., an average of 20 minutes or greater of WASO, excluding terminal WASO). If insomnia participants do not meet either of these established quantitative criteria, they will be excluded from the study. Actigraphy will be used to confirm classification and to further rule out any participant who has a circadian rhythm disorder (i.e., regular sleep phase occurring out of the range of 9pm-9am).

